9.6 Data Analyses.....	30
10. DATA COLLECTION AND QUALITY ASSURANCE.....	30
10.1 Data Collection Forms	30
10.2 Data Management	31
10.3 Quality Assurance	31
10.3.1 Training.....	31
10.3.2 Protocol Deviations.....	31
10.3.3 Monitoring.....	31
11. PARTICIPANT RIGHTS AND CONFIDENTIALITY.....	32
11.1 Institutional Review Board (IRB) Review	32
11.2 Informed Consent Forms	33
11.3 Participant Confidentiality	33
11.4 Study Discontinuation.....	34

Tool Revision History

Version: 11.0

Version Date: 5.8.2020

12. POTENTIAL BENEFITS	34
12.1 Potential Benefits to Participating Individuals	33
12.2 Potential Benefits to Society	33
13. REFERENCES.....	33
14. SUPPLEMENTS/APPENDICES.....	40

Tool Revision History

Version: 11.0

Version Date: 5.8.2020

STUDY TEAM ROSTER – key personnel

[name], PhD, MPH, Principal investigator

[name], PhD, Co-investigator, MGH site PI

[name], Co-investigator

[name], Research coordinator

PRÉCIS

Study Title

Physiologic and Behavioral Correlates of GERD Symptom Severity

Objectives

Primary Aim: To identify the physiologic responses associated with improvement in gastroesophageal reflux disease (GERD) symptom severity in response to two different types of patient-provider interactions.

Secondary Aim: To determine whether an expanded patient-provider visit modeled after an integrative medicine consultation leads to more supportive provider behaviors and improved rapport, engagement, and reciprocity in the patient-provider interaction.

Design and Outcomes

This is a pilot, proof-of-concept randomized controlled trial to assess the physiologic and behavioral mechanisms associated with improved symptom severity in adult patients with GERD-related symptoms in response to enhanced patient-provider interactions.

Subjects will be randomized to receive one of two different semi-scripted visit types – either a “standard visit” modeled after an empathic, conventional primary care evaluation or an “expanded visit” modeled after an integrative medicine consultation. During the visit we will measure heart rate variability (HRV) and galvanic skin response (GSR) in the patient-provider dyads; in addition, we will video record the interactions for later analysis of behavioral responses. Subjects will also complete a daily GERD symptom diary and questionnaires about GERD symptoms before their visit with a study provider and two weeks later. Blood will also be drawn and frozen for later omics-based analyses.

Interventions and Duration

Subjects will have a single visit with a “study provider,” a physician or nurse practitioner who they have never previously met. Subjects will complete a daily symptom diary for 2 weeks following this visit and return for a second study-related visit in which they will complete questionnaires and be debriefed by a physician on the study team (not the individual who conducted the study intervention visit).

Sample Size and Population

We plan to enroll to obtain 24 completing subjects with GERD, age 21-70 with heartburn symptoms 3 or more days per week. To permit a spread of physiologic, behavioral, and symptom responses, 16 subjects will be randomized to the expanded visit intervention and 8 subjects will be randomized to the standard visit intervention (2:1 expanded:standard

Tool Revision History

Version: 11.0

Version Date: 5.8.2020

randomization). We will stratify randomization by study provider such that each provider will see 6 subjects (4 expanded visits and 2 standard visits).

1. STUDY OBJECTIVES

The patient-provider relationship is central to the art of medicine and affects a range of health outcomes. However, the specific benefits, and exact mechanisms, by which this relationship supports the healing process is poorly understood. Emerging data suggests that physiologic biomarkers such as galvanic skin response (GSR) and heart rate variability (HRV) are associated with empathy and correlated with the complex verbal and non-verbal behaviors of patients and providers during an encounter. Physiologic synchrony in patient-provider dyads and supportive non-verbal behaviors may be associated with subsequent health outcomes. This pilot study will test these hypotheses using GERD as a model condition.

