Social psychologists have developed and validated a variety of coding schemes to analyze providers’ verbal and non-verbal behaviors and to link these behaviors with patient satisfaction, understanding, trust, rapport, empathy, and a variety of related factors [9,55–60]. This rich literature has yielded many insights and a variety of tools used in studies of physician-patient communication, but rarely have these tools been linked with physiology or health outcomes [7].

I recently found that an “expanded” provider visit modeled after a visit to an IM provider was more effective in decreasing heartburn and dyspepsia symptoms in patients with GERD than a “standard” provider visit modeled after an empathic conventional medical visit [61]. I used a script of pre-determined questions for each visit type. The standard visit script included questions about GERD history, symptoms, prior evaluation and treatments, and past medical history. The expanded visit script included the same questions plus additional questions that inquired about their GI symptoms, non-GI symptoms, and overall temperament. Thus, the main differences between the visits were the length of time spent with the subject and the additional questions that were asked. Many of the subjects in this study were already taking pharmaceutical medications for GERD, suggesting that symptom improvement resulting from the expanded provider visit may enhance the efficacy of some medications in providing adequate symptom relief.

While some may argue that increasing visit length is impractical in conventional healthcare settings, one reason why payers will not adequately reimburse for increased visit lengths is the lack of data linking visit length with health outcomes. Increased visit length has been associated in clinical practice with reduced number of prescriptions and

Tool Revision History

Version: 11.0

Version Date: 5.8.2020

increased patient satisfaction, engagement, and quality of care [62–64]. Other studies suggest mechanisms by which provider communication (verbal & non-verbal) may affect health outcomes [65]. Yet we really do not know what makes longer visits more effective. By first better understanding the mechanisms that make the expanded visit intervention effective, I will be able to make informed decisions regarding future changes to this intervention and adaptations that may make it more feasible in today's healthcare environment.

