9.5.2 Secondary Outcomes

1. The difference in the frequency of supportive provider behaviors between the standard and expanded visit groups.
2. The difference in the ratings of rapport, engagement, and reciprocity between the standard and expanded visit groups.

Tool Revision History

Version: 11.0

Version Date: 5.8.2020

The number of nonverbally supportive behaviors and impression ratings of the patient-provider interaction will come from coding of video recordings of the patient provider interactions (study visit 1).

We hypothesize that the frequency/intensity of supportive provider behaviors increases as the expanded visit unfolds, compared to the standard visit, as rapport, engagement, and reciprocity between patient and provider increase. Briefly, thin slices (1.5 minutes) of video occurring near the beginning and end of the standard visit (and also a time point in the middle of the expanded visit roughly equivalent to the end of the standard visit) will be analyzed by trained coders, blinded to the study hypotheses, for the presence of 1) micro-level nonverbally supportive behaviors (e.g., friendly voice quality, leaning forward, open body posture, eye contact, nod, smile, and gestures) as well as 2) macro-level impression ratings of the interaction (e.g., rapport, engagement, reciprocity).

The PI will meet weekly with the coders to review findings and resolve areas of disagreement until greater than 80% concordance is achieved between coders. Frequency of supportive behaviors and ratings of interactions will be compared using generalized linear mixed models as appropriate for each outcome (e.g., occurrence of binary events, counts of discrete events, ordinal ratings of rapport or engagement). The models will include terms for time-point, visit group assignment, and their interaction.

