12.2 Potential Benefits to Society

This study will provide insights on the physiologic and behavioral mechanisms that result in improved health outcomes from enhanced patient-provider relationships that may be applicable to a range of different medical conditions.

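### Section 1 says the pilot will test whether supportive non-verbal behaviours are associated with health outcomes, but no planned analysis relates video-coded behaviour to GERD symptom change

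*Combined protocol and SAP*

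**What the plan says.** Section 1 names two candidate correlates of later health outcomes and commits the pilot to testing them: "Physiologic synchrony in patient-provider dyads and supportive non-verbal behaviors may be associated with subsequent health outcomes. This pilot study will test these hypotheses". The précis, under Design and Outcomes, describes the trial's purpose in similar terms: "to assess the physiologic and behavioral mechanisms associated with improved symptom severity". The rationale in section 2.2 says of behaviour-coding tools that "rarely have these tools been linked with physiology or health outcomes". Section 12.2 tells the reader: "This study will provide insights on the physiologic and behavioral mechanisms that result in improved health outcomes".

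The formal secondary objective (section 1.2) is narrower. It asks whether the expanded visit produces more supportive provider behaviour and better rapport, engagement and reciprocity. Section 9.5.2 implements that objective: "Frequency of supportive behaviors and ratings of interactions will be compared using generalized linear mixed models as appropriate for each outcome". The model terms given there are time-point, visit group and their interaction. The video row of the section 9.5 table says the same.

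Section 9.6 lists possible modifiers of symptom improvement: perceived stress, perceived empathy, personality, gender and race. The section 9.5 table adds the HEAL patient-provider connection. Coded behaviour is in neither place.

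**The concern.** A comparison of behaviour between visit types answers whether the longer visit changes what providers do. It does not answer whether subjects who met more supportive behaviour improved more, which is the association that section 1 says will be tested. The two questions can have different answers. Behaviour could differ between visit types and be unrelated to symptoms, or be similar on average in both types and still vary between dyads in a way that tracks symptoms.

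The second case is plausible here. Section 5.1 tells providers to keep empathy equal in both groups and names eye contact as part of that. Eye contact is also one of the coded behaviours in section 9.5.2. The design therefore works to equalise part of what the group comparison measures, while the variation between dyads goes unused.

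At stake is one stated hypothesis of the pilot. Section 9.2 gives the study's aim as finding features to carry into later work. Without a link from behaviour to symptoms, the trial would report which behaviours differ by visit type and nothing about which of them go with improvement.

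**Working it through.** **Step 1. Match each promise to an analysis.**

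| Link | Where promised | Where analysed |
|---|---|---|
| Synchrony and symptom change | Section 1; 9.1 primary hypothesis 1 | 9.5.1, Pearson correlation |
| Within-subject GSR or high-frequency HRV change and symptom change | 9.1 primary hypothesis 2 | 9.5.1, Pearson correlation |
| Coded behaviour and ratings by visit type and time within the visit | 1.2; 9.1 secondary hypothesis | 9.5.2, mixed models |
| Patient-reported empathy and connection (CARE, HEAL) and symptom change | 9.5 table; 9.6 (empathy) | Generalized linear models |
| Coded supportive behaviour and symptom change | Section 1; précis | None |

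The last row is empty in 9.1, the 9.5 table, 9.5.1, 9.5.2 and 9.6.

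**Step 2. Could existing analyses be combined to supply it?** The listed primary and secondary outcomes contain no between-group comparison of symptom change. Even if behaviour and symptoms both differed by visit type, visit length and the extra questions differ too, so the behaviour-symptom association would still not be shown.

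**Step 3. Reproduce the plan's figures.** The missing analysis has no stated figure. The nearest are those in 9.2, given for physiologic concordance against symptoms with 24 dyads. Fisher's z has SE = 1/√(24 − 3) = 0.218.

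- P(r > 0.20 if ρ = 0.36): atanh(0.36) = 0.377, atanh(0.20) = 0.203, and (0.377 − 0.203)/0.218 = 0.80, giving 0.788. With the bias term ρ/(2(n − 1)) it is 0.798, and by simulation 0.800. The plan says 80%.
- Power at ρ = 0.54, two-sided α = 0.05, critical r = 0.404: 0.789 by Fisher's z, 0.804 with the bias term, 0.808 by simulation. The plan says 80%.

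The plan's figures are sound.

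**Step 4. What the missing correlation would offer, unadjusted, with independent dyads.**

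- If ρ = 0.36, the chance of r > 0.20 is about 80%, as above.
- If ρ = 0, the chance of r > 0.20 is about 17% (simulation 0.174).
- An observed r = 0.20 has a 95% CI of tanh(0.203 ± 1.96 × 0.218) = −0.22 to 0.56.
- An observed r = 0.36 has a 95% CI of −0.05 to 0.67.

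**Step 5. The same with adjustment.** Assume one parameter for visit type and three for four providers. For a partial correlation, SE = 1/√(24 − 4 − 3) = 0.243.

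- If the partial ρ = 0.36: (0.377 − 0.203)/0.243 = 0.72, giving about 76%.
- If the partial ρ = 0: 0.203/0.243 = 0.84, giving about 20%.

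The 9.2 figures therefore do not carry over unchanged to the adjusted version.

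**Step 6. Chance passes.** Two scores, each from two choices of slice, give four unadjusted coefficients. If all true correlations were zero, the chance that at least one exceeds 0.20 is 1 − (1 − 0.174)² = 32% for two independent coefficients and 1 − (1 − 0.174)⁴ = 53% for four. Positive correlation between the scores pulls these towards 17%.

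**The case against.** The strongest reply is that the conflict sits in introductory text. The formal objectives in 1.1 and 1.2, repeated as aims in the précis, do not include a behaviour-symptom link, and 9.1, 9.5 and 9.5.2 implement those objectives faithfully. The title, the literature remark in 2.2 and the benefits statement in 12.2 are not analytic commitments. On this view, editing one sentence closes the gap. Much of this stands, and it is why narrowing the wording is an acceptable repair. But section 1 does say that the pilot will test the hypothesis. The précis also justifies the 2:1 allocation partly by a spread of behavioural and symptom responses, although 9.1 gives only the range of physiologic concordance as the reason.

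A second reply is that 24 subjects are too few. That is the number accepted for the primary correlations, and it argues for exploratory labelling rather than omission.

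Three stronger readings are tempting, and the documents do not support them.

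- A reader might infer that the video data are compared only between visit types. In fact 9.1 and 9.5.2 also compare time-points within visits.
- A reader might infer that nothing about the relationship is set against symptoms. CARE and HEAL are, which narrows the gap without closing it.
- A reader might infer that a test of behaviour against GSR or HRV was also promised. Section 1 offers that link as background from emerging data. The hypotheses it says will be tested are most naturally those of the next sentence: "Physiologic synchrony in patient-provider dyads and supportive non-verbal behaviors may be associated with subsequent health outcomes".

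**Conclusion.** The point holds. Section 1 and the précis undertake to relate provider behaviour to symptom outcome, and no analysis in the supplied text does so. The size is one stated hypothesis left without an analysis. The primary correlations and the secondary group comparisons are unaffected, so this is a worthwhile and cheap improvement rather than a flaw in the main results.

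The conclusion rests on the protocol text alone; the appendices are listed but their content is not supplied. The figures of about 80% (ρ = 0.36) and about 17% (ρ = 0) for r > 0.20 assume 24 complete subjects with codable video, bivariate normality, independent dyads and no adjustment. Independence is doubtful, because about four providers each see six subjects and provider behaviour may vary mainly between providers. The documents give no intra-provider correlation from which to quantify this.

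It would go too far to expect the added analysis to settle which behaviours matter. A pooled score cannot separate them, and the intervals at this sample size are wide.

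**What to change.** Add to 9.5.2 and to the video row of the 9.5 table an analysis labelled exploratory:

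1. Define in advance one supportive-behaviour score and one interaction-rating score per subject, for example the mean of the standardised coded behaviours and the mean of rapport, engagement and reciprocity.
2. Name the slices. Include the late slice of each visit as well as the time-matched slices. Time-matched slices alone would drop the late part of the expanded visit, where 9.1 and 9.5.2 expect supportive behaviour to rise.
3. Relate each score to change in GERD symptom severity as defined in 9.5.1.
4. Report estimates with 95% confidence intervals, unadjusted and with visit type and provider in the model. Apply the 9.2 figures to the unadjusted correlation only, and state the independence assumption.
5. Report individual behaviours descriptively, so that the pooled score does not hide them.

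Correlating behaviour with GSR or HRV concordance is optional.

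The cost is plan wording and a few extra coefficients on data already collected and coded. The downside is more chance findings, as sized in step 6 of the working, which is why the exploratory label and the advance definition of scores and slices are needed.

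If the sponsor does not want this analysis, limit the wording in section 1, the précis and section 12.2 to the comparison of behaviour by visit type and time-point.

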1.1 Primary Objective

To identify the physiologic responses associated with improvement in GERD symptom severity in response to two different types of patient-provider interactions.

1.2 Secondary Objective

To determine whether an expanded patient-provider visit modeled after an integrative medicine consultation leads to more supportive provider behaviors and improved rapport, engagement, and reciprocity in the patient-provider interaction.

2. BACKGROUND AND RATIONALE

2.1 Background on Condition, Disease, or Other Primary Study Focus

The patient-physician relationship is central to the art of medicine [1,2]. The quality of this relationship affects a range of health outcomes, from irritable bowel [3] and cold symptoms [4] to blood pressure, pain levels, and diabetes outcomes [5–8]. However, the specific benefits, and exact mechanisms, by which this relationship supports healing remain poorly understood. Previous work has demonstrated that when providers maintain eye contact, actively listen, and express empathy, their patients improve more after receiving a placebo than patients receiving care from apparently more detached providers [3,4]. Though studies have suggested a role for communication skills and both cognitive and emotional components of empathy, the variety of measures used and lack of clarity in definitions have limited the interpretation of this work [5,6,9,10].

In most conventional medical settings, practice demands have resulted in reduced time to focus on relational aspects of care. Concomitantly, medical educators and professional societies have called for greater emphasis on humanism, patient-centered care, and improved patient-provider communication [11,12]. Indeed, patients are frequently stressed/in distress when they visit a physician [13]. Perceived lack of time and anxiety about the visit likely contributes to this stress, one manifestation of which is white coat hypertension [14].

Tool Revision History

Version: 11.0

Version Date: 5.8.2020

The public has become increasingly interested in complementary and integrative medicine (IM) healing approaches in which patient-provider dynamics often differ substantially from most conventional medical visits [15–19]. IM providers frequently spend more time with patients and ask questions that are quite different from those asked during conventional visits. The IM consultation process may produce enhanced placebo effects [19]. It is unclear whether these effects represent a form of interpersonal healing [20], an enhanced patient-provider relationship (e.g., increased perceived empathy or trust), or simply provide patients with the opportunity to reflect on their symptoms in a safe and non-judgmental space (a form of therapeutic narrative medicine [21]) creating an openness to perceiving symptoms differently and enhancing coping [22]. Some patients feel “more heard” by IM providers [23]. IM providers may make patients feel more “at ease” and relaxed, promoting a physiologic response (e.g., reduced heart rate and blood pressure) similar to that elicited by meditation and other mind body techniques [24]. Feeling less stressed during a medical visit may create an openness to change and improved memory of, and follow-through with, the provider’s recommendations [25]. Yet there are few studies of these interactions and they largely rely upon patient interviews or responses to surveys [15–18].

[figure not shown]
Gastroesophageal reflux disease (GERD) is one of the most prevalent health-related conditions in the Western world with prevalence estimates ranging from 20-40% [26,27]. GERD is primarily a clinical diagnosis, characterized by symptoms of heartburn and acid reflux. It is associated with decreased health-related quality of life and significant healthcare costs and lost productivity [28,29]. Standard treatment includes antacids, H2 receptor blockers, and proton pump inhibitors (PPIs), with the latter generally regarded as the most effective of these therapies. Nonetheless, many patients experience continued symptoms despite taking PPIs [30]. Many patients who do not find relief with PPIs have functional heartburn symptoms and/or co-occurring dyspepsia symptoms (e.g., upper abdominal discomfort, bloating, and gas) that do not respond well to this class of medication [31,32]. Moreover, awareness of the interconnections between the central nervous and gastrointestinal systems has led to the recognition that stress can profoundly affect gastrointestinal (GI) symptoms, such as GERD [33], suggesting that interventions targeting these pathways may improve symptoms [34]. Notably, the placebo response rate in trials of GERD medications can be as high as 40% [35].

2.2 Study Rationale

Recent studies are beginning to reveal the neural correlates of empathy, both in general [36] and in patient-provider relationships [37,38]. Activation of specific neural pathways drives changes in autonomic nervous system regulation [39], resulting in downstream changes in physiologic

biomarkers such as galvanic skin response (GSR) and heart rate variability (HRV) [40,41]. A growing body of research has identified concordance in physiologic biomarkers between individuals. An excellent review of this topic, also known as “interpersonal autonomic

Figure 1: Proposed model for mechanisms underlying the patient-provider relationship

Tool Revision History

Version: 11.0

Version Date: 5.8.2020

physiology” or “physiologic synchrony,” has recently been published [42]. The authors reviewed 61 studies covering relationships between therapist and client, couples, mother and child, teammates, and other relationships. There were 8 studies of the therapist-client relationship which examined either heart rate (HR) or skin conductance/galvanic skin response (GSR). Multiple studies found positive correlations between empathy ratings and physiologic synchrony. The study I have proposed would be the first to examine physiologic biomarkers in the context of physician-patient interactions in a medical setting.

As illustrated in Figure 1 above, we hypothesize that moment-to-moment autonomic changes in patients and providers over the course of a visit collectively influence perceptions of the encounter (part of the “neural response”) and response to treatment and that improved treatment response is associated with increased concordance in these autonomic changes.

GSR and HRV can also be used to assess relative physiologic stress vs. relaxation [43]. Typically GSR and HR decrease and high frequency HRV increases in the relaxed state [24,44,45]. While empathic visits may theoretically reduce patients’ allostatic load and distress [46], this hypothesis has not been studied rigorously. Newer computational approaches incorporating complexity theory to the analysis of physiologic data [47] have yielded valuable insights to the study of human disease (e.g., decreased HRV is associated with increased cardiovascular mortality [48,49]) and the effects of integrative modalities such as tai chi [50,51]. There is limited data using these approaches to study client-therapist interactions [52–54].

Social psychologists have developed and validated a variety of coding schemes to analyze providers’ verbal and non-verbal behaviors and to link these behaviors with patient satisfaction, understanding, trust, rapport, empathy, and a variety of related factors [9,55–60]. This rich literature has yielded many insights and a variety of tools used in studies of physician-patient communication, but rarely have these tools been linked with physiology or health outcomes [7].

I recently found that an “expanded” provider visit modeled after a visit to an IM provider was more effective in decreasing heartburn and dyspepsia symptoms in patients with GERD than a “standard” provider visit modeled after an empathic conventional medical visit [61]. I used a script of pre-determined questions for each visit type. The standard visit script included questions about GERD history, symptoms, prior evaluation and treatments, and past medical history. The expanded visit script included the same questions plus additional questions that inquired about their GI symptoms, non-GI symptoms, and overall temperament. Thus, the main differences between the visits were the length of time spent with the subject and the additional questions that were asked. Many of the subjects in this study were already taking pharmaceutical medications for GERD, suggesting that symptom improvement resulting from the expanded provider visit may enhance the efficacy of some medications in providing adequate symptom relief.

While some may argue that increasing visit length is impractical in conventional healthcare settings, one reason why payers will not adequately reimburse for increased visit lengths is the lack of data linking visit length with health outcomes. Increased visit length has been associated in clinical practice with reduced number of prescriptions and

Tool Revision History

Version: 11.0

Version Date: 5.8.2020

increased patient satisfaction, engagement, and quality of care [62–64]. Other studies suggest mechanisms by which provider communication (verbal & non-verbal) may affect health outcomes [65]. Yet we really do not know what makes longer visits more effective. By first better understanding the mechanisms that make the expanded visit intervention effective, I will be able to make informed decisions regarding future changes to this intervention and adaptations that may make it more feasible in today's healthcare environment.

